8.7 Prior and Concomitant therapy

For patients with treatment failure who have received antibiotics for less than 72 hours the information on therapy should be obtained and recorded in the eCRF (i.e., the trade name, INN/name of active ingredients, dosage, date of start, termination date).

The information on prior/concomitant drugs (the trade name, INN/name of active ingredients, dosage or change of dosage, indication, frequency of intake, prescription method, date of start, termination date) which the patient took before and takes during the study, should be registered in the corresponding section of the eCRF. All subsequent changes of concomitant therapy during the study should also be reflected in the eCRF. It will document information on previous drugs and treatments used from the onset of community-acquired pneumonia until the enrollment in the study (signing of the Informed Consent Form).

If there are any questions regarding concomitant therapy, the study Medical Adviser (see CONTACT information) should be contacted.

CONFIDENTIAL Page 41 of 88

8.7.1 Permitted concomitant therapy

Females enrolled in study who use oral contraceptives can continue to take these drugs during whole study.

Patients are prohibited from using other drugs, except for necessary medical requirements, including:

- Treatment of concomitant pathology if it is not an exclusion criterion. In that case usual treatment regimen shouldn't contain prohibited drugs (see Section 8.7.2)
- Symptomatic treatment of the CAP (e.g., drugs such as antipyretics, analgesics, antihistamines, or cough suppressants) within the first 2 days of the treatment if necessary required by the opinion of the investigator. Since Day 3 (including) of the therapy these drugs are prohibited (see Section 8.7.2).

Information about all the concomitant drugs should be documented in the electronic Case Report Form (eCRF) in details (see Section 8.7).

8.7.2 Prohibited and limited in use therapy

During treatment period (from Visit 1 to Visit 3) the following medications should be prohibited:

- 1. Antacids, multivitamins containing calcium, magnesium, iron, zinc, or aluminum, and sucralfate should be prohibited within 3 hours before and after oral administration of the investigational drug. Intravenous therapy should not be coadministered with any solution containing multivalent cations, e.g., magnesium, through the same intravenous line.
- 2. Probenecid.

During study period (from Visit 1 to Visit 5) the following medications should be prohibited:

- 1. Drugs that may prolong the QT interval with known risk or possible risk of Torsades de Pointes (TdP). The list of these drugs is presented in Appendix 3.
- 2. Chemotherapeutic agents or antitumor drugs.
- 3. Other systemic antibacterial drugs (except for treatment failure).
- 4. Systemic immunosuppressive drugs, including inhaled steroids.
- 5. Drugs that may act to alter the signs and symptoms of infections (e.g., antipyretics, analgesics, antihistamines, or cough suppressants) since day 3 (including) of the treatment.
- 6. Investigational products other than studied in this trial and other than the patient has been randomized.

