3.4 Assessment of Potential risks and benefits for participants

Comparator Tavanic[®] (Levofloxacin) is effective antibiotic approved for treatment of a wide variety of infectious diseases, including CAP. The drug may be administered for empiric antimicrobial therapy in patients with CAP.

Investigational product Nemonoxacin, capsules, has already been approved in Taiwan and China for treatment of CAP and the phase III clinical study of efficacy and safety of Nemonoxacin intravenous formulation is ongoing. At this time more than 1000 subjects were participated in various clinical studies of nemonoxacin, capsules or solution for infusion.

Nemonoxacin has shown similar clinical and microbiological efficacies as compared with levofloxacin during clinical studies in patients with CAP (see Sections 3.3.2.2 and 3.3.2.3). Nemonoxacin was well tolerated and had acceptable safety profile either when administered by intravenous and oral routs. The majority of AEs reported during the studies were mild and transient.

The risk to patients in this clinical study will be minimized by compliance with selection criteria. Taking into account available safety data for investigational medicinal products, both Levofloxacin and Nemonoxacin (e.g., possibility of QT prolongation, hypoglycemia, tendinitis and tendon rupture, etc.), these medicinal products will be avoided in patients with renal impairment, diabetes mellitus, QT prolongation, uncorrected hypokalemia, receiving class Ia or III antiarrhythmic agents, receiving corticosteroids, etc.

Levofloxacin was shown to have photosensitization activity. Therefore, in order to prevent photosensitization in patients the Patient Information Leaflet provides precautions for study participants not to expose themselves unnecessarily to strong sunlight or to artificial ultra-violet rays. Although Nemonoxacin did not elicit cutaneous phototoxicity in preclinical studies and by now there is no clinical data suggested phototoxicity of the drug the aforementioned precautions will be taken by all participants (i.e., regardless of treatment group) because of double-blind design of the study and because of absence of certainty the drug has not such activity.

In consideration of the foregoing assumptions the risk-benefit ratio for the participants is acceptable.

This clinical study will be conducted in compliance with the Protocol, ICH GCP and all other applicable local regulatory requirements.

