7.2 Exclusion Criteria

Patients won't be eligible for inclusion in the study if any of the following exclusion criteria is applied:

- 1. Known hypersensitivity to quinolones, fluoroquinolones or any of the excipients.
- 2. Female patients who are pregnant or nursing.
- 3. History of tendon disease/disorder related to quinolone treatment.
- 4. Known congenital or documented-acquired QT/QTc(F) prolongation on ECG (QTc(F) interval more than 450 ms); concomitant use of drugs, reported to increase the QT interval; uncorrected hypokalaemia and uncorrected hypomagnesemia; clinically relevant bradycardia; clinically relevant heart failure

CONFIDENTIAL Page 35 of 88

- with reduced left-ventricular ejection fraction; previous history of symptomatic arrhythmias.
- 5. History of bronchiectasis, cystic fibrosis, bronchial obstructions excluding chronic obstructive pulmonary disease.
- 6. History of epilepsy and/or history of psychotic disorder.
- 7. Patients with history of myasthenia gravis
- 8. Patients with diabetes mellitus
- 9. Known glucose-6-phosphate dehydrogenase deficiency.
- 10. Active hepatitis or decompensated cirrhosis.
- 11. Alanine transaminase or aspartate transaminase increase > 3 fold ULN.
- 12. Patients with creatinine ≥ 1.1 fold ULN.
- 13. Patients requiring concomitant systemic or inhaled antibiotics (e.g., tobramycin).
- 14. Known or suspected active tuberculosis or endemic fungal infection.
- 15. Concomitant immunosuppressive therapy including a long-term (more than 2 weeks) treatment with oral or intravenous glucocorticoids at doses of 20 mg and higher of prednisone daily or an equivalent dose of other glucocorticoids.
- 16. Patients known to have HIV-positive status or AIDS or known to have other disease that seriously affects the immune system such as active haematological or solid organ malignancy, or splenectomy.
- 17. History of drug or alcohol abuse.
- 18. Patients have received quinolones or fluoroquinolones within 14 days before enrollment.
- 19. Previous enrolment in this study or participation in another study within the previous 4 weeks.
- 20. Patients with any severe medical condition as determined by medical history that, in the opinion of the investigator, does not allow the patient to carry out all planned procedure of the protocol.

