APPENDIX 1: CRITERIA FOR HOSPITALIZATION*

Criteria for hospitalization in patients with a confirmed diagnosis of community-acquired pneumonia*

Patients require hospitalization if they comply with **at least one** of the following criteria:

- 1. Physical examination data:
 - Respiratory rate \geq 30 breaths per minute
 - Diastolic blood pressure ≤60 mm Hg
 - Systolic blood pressure <90 mm Hg
 - Heart rate ≥125 beats per minute
 - Temperature < 35.5°C or ≥ 39.9 °C
- 2. Laboratory data and X-ray findings:
 - WBC count of $< 4.0 \times 10^9 / L$ or $> 20.0 \times 10^9 / L$
 - SaO₂ <92% (measured by pulse oximetry)
 - PaO₂ <60 mm Hg and/or PaCO₂ >50 mm Hg while breathing room-air
 - Serum creatinin >176.7 μ mol/l or blood urea nitrogen >7.0 mmol/l (blood urea nitrogen = urea, mmol/l/2.14)
 - Pneumonic infiltration, involving more than one lobe
 - Cavitation in a lung
 - Pleural effusion
 - Rapid progression of focal-infiltrative lesions in the lungs (> 50% increasing of infiltration size within the previous 2 days)
 - Hematocrit <30% or hemoglobin <90 g/l
 - Extrapulmonary site of infection (meningitis, septic arthritis and other)
 - Sepsis or multiple organ failure, manifested as metabolic acidosis (pH <7.35), coagulopathy
- 3. Impossibility of adequate care and fulfillment of all medical prescriptions at home

Criteria for preferred inpatient treatment for patients with a confirmed diagnosis of community-acquired pneumonia*

Preferred in-patient treatment may also be considered in the following cases:

- 1. Older than 60 years of age
- 2. Concomitant diseases (chronic bronchitis, chronic obstructive pulmonary disease, bronchiectasis, malignancies, diabetes mellitus, chronic renal insufficiency, congestive cardiac failure, chronic alcoholism, drug abuse, significant weight deficit, cerebrovascular diseases)
- 3. Treatment failure after starting treatment with antibiotics
- 4. The desire of the patient and/or his/her family.

CONFIDENTIAL Page 74 of 88

Criteria for Intensive Care Unit treatment for patients with a confirmed diagnosis of community-acquired pneumonia**

The patients require hospitalization in an intensive care unit (in that case the patient will not be enrolled in the study) **if one of** the following major criteria is met:

- Severe respiratory insufficiency requiring mechanical ventilation;
- Septic shock requiring the administration of vasopressors;

OR if the patient meets **three** of the following minor criteria at the same time:

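### A COPD patient on an inhaled steroid is eligible under section 7.2, but section 8.7.2 prohibits that steroid from Visit 1, and section 3.4 states a third steroid rule

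*Combined protocol and SAP*

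**What the plan says.** Eligibility. Exclusion 15 in section 7.2, repeated in the synopsis, covers "Concomitant immunosuppressive therapy including a long-term (more than 2 weeks) treatment with oral or intravenous glucocorticoids at doses of 20 mg and higher" (prednisone or equivalent). No exclusion criterion mentions inhaled steroids. Exclusion 5 reads "History of bronchiectasis, cystic fibrosis, bronchial obstructions excluding chronic obstructive pulmonary disease", so COPD is spared. In Appendix 1, on which inclusion criterion 3 relies, the second ground for preferred inpatient treatment begins "Concomitant diseases (chronic bronchitis, chronic obstructive pulmonary disease".

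Prohibited therapy. Section 8.7.2 opens its second list with "During study period (from Visit 1 to Visit 5) the following medications should be prohibited", and item 4 of that list is "Systemic immunosuppressive drugs, including inhaled steroids". It gives no dose, no duration and no exception for maintenance use.

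Risk control. Section 3.4 first says that risk is limited by keeping to the selection criteria. It then lists groups in whom the study drugs will be avoided, ending with patients "receiving class Ia or III antiarrhythmic agents, receiving corticosteroids, etc".

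Connecting text. Section 8.7.1 allows treatment of a comorbidity that is not an exclusion, provided the usual regimen contains nothing prohibited by 8.7.2. Section 8.7 refers questions on concomitant therapy to the study Medical Adviser. Section 12.2 gives taking a prohibited drug as an example of a major deviation. Patients with a major deviation leave the CE and BE efficacy analyses but stay in mITT, b-mITT and the safety population.

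**The concern.** A site that screens a COPD patient on a maintenance inhaled steroid finds no criterion in 7.2 that keeps the patient out. Once the patient is enrolled, the same medicine is prohibited from the first day. Section 3.4 meanwhile tells an ethics committee or regulator that the selection criteria deal with corticosteroid use in general, which the criteria as worded do not do.

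Two things are at stake. First, the protocol describes a risk control that its own eligibility rules do not deliver, and it gives no instruction on steroid use that is ongoing at entry. Second, membership of CE and BE can turn on how a site handles a conflict that the protocol itself created. CE matters here because it carries the supportive non-inferiority analysis in section 12.6.3.

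**Working it through.** The plan gives no figure on this point, so there is none to reproduce. The check is to read the three rules side by side for three kinds of patient.

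| Patient at entry | 7.2 (exclusions 5 and 15) | 8.7.2 item 4 | 3.4 |
|---|---|---|---|
| COPD, inhaled steroid | Eligible: route not named, COPD spared | Prohibited by name | Avoided, since no route is given |
| Oral or i.v. glucocorticoid, below 20 mg or for 2 weeks or less | Outside the named case; whether it still counts as immunosuppressive therapy is open | No dose given; inhaled steroids are included, so oral use is hard to leave out, but it is not named | Avoided as worded |
| Oral or i.v., more than 2 weeks, 20 mg or above | Excluded | Prohibited | Avoided |

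The three sections clearly agree only in the last row. The first row is a plain mismatch. The second is an ambiguity.

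Next, does any other text close the first row? Section 8.7.1 says what a comorbidity regimen should not contain. It is not an eligibility criterion, and it does not say what happens to a drug already in use. The Medical Adviser contact in 8.7 is a route for questions, not a rule.

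Two outcomes remain for the enrolled patient:

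1. The inhaled steroid continues. This is intake of a prohibited drug, hence a major deviation under 12.2. The patient leaves CE and BE and stays in mITT, where section 12.6.2 places the primary analysis.
2. The inhaled steroid stops. A maintenance medicine is withdrawn at entry. With treatment lasting 7 to 14 days and Visit 5 falling 21 to 23 days after the last dose, the prohibition runs to between Day 7 + 21 = 28 and Day 14 + 23 = 37.

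Elsewhere the protocol does pair the two kinds of rule. QT-prolonging drugs appear in both exclusion 4 and 8.7.2, and other systemic antibacterials in both exclusion 13 and 8.7.2. For steroids the pairing is only partial.

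**The case against.** The strongest reply is that the sections can be read together. Nothing obliges a site to enrol everyone who passes 7.2. Section 8.7.1 signals that a patient whose usual regimen contains a prohibited drug is a poor fit, and the Medical Adviser can be asked. Exclusion 15 also says that immunosuppressive therapy is excluded *including* the long-term, higher-dose case. If immunosuppressive is read as broadly there as in 8.7.2, the gap closes.

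Part of this stands. A reader might infer that sites must enrol such patients; the documents say only that they may. A reader might also infer that a patient on low-dose prednisone is certainly eligible and certainly in breach. That requires a narrow reading in 7.2 and a broad one in 8.7.2, so it is an ambiguity and not a fact. The broad reading of exclusion 15 is nonetheless strained, because it leaves the stated route, dose and duration with nothing to do. To reach inhaled steroids, a site would have to import the wording of another section.

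Section 3.4 is background narrative. Its list is open-ended, it says avoided and not excluded, and it does not tie corticosteroids to any one of the risks it mentions. It still presents the list as the product of the selection criteria, so it should match them. Appendix 1 is weak evidence of whom the trial means to enrol, since the same list includes conditions that 7.2 excludes, such as diabetes. The eligibility of COPD patients rests on exclusion 5.

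**Conclusion.** The inconsistency is real and sits in current text. For inhaled steroids in COPD it follows from the wording of 7.2 and 8.7.2. For oral or intravenous glucocorticoids below the exclusion 15 threshold the text is unclear. The documented statistical consequence is confined to the supportive CE and BE sets, and arises only if the steroid is continued; the primary mITT analysis keeps these patients.

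Two stronger readings are tempting and lack support. One is that stopping the steroid would distort the primary endpoint through respiratory symptoms. No passage says so, and with 1:1 double-blind allocation such an effect would be expected in both arms, so no bias in the treatment difference is shown. The other is a patient count. If 10 to 20% of the 342 randomised had COPD or needed long-term steroids, and half of those used an inhaled or low-dose steroid, the result would be 342 × 0.10 × 0.5 ≈ 17 to 342 × 0.20 × 0.5 ≈ 34. Both shares are assumptions with no source in the documents, and the sum presumes that every such patient continues the steroid. The number affected is unknown, and the finding does not depend on it.

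**What to change.** Reconcile exclusions 5 and 15 in section 7.2, their copy in the synopsis, sections 8.7.1 and 8.7.2 item 4, and section 3.4, so that all describe the same steroid use by route, dose and duration. The test is that no patient eligible under 7.2 is in breach at Visit 1. This can be met by bringing eligibility into line with the prohibition or the prohibition into line with eligibility, with 3.4 then describing the restriction that actually applies. The clinical choice is the sponsor's. The text should also say how steroid use ongoing at entry is handled, and whether it counts as a major deviation for CE and BE.

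The cost is amendment wording in a few places. No new data are needed, because section 8.7 already has prior and concomitant drugs recorded with dosage and dates. If eligibility is tightened, some steroid-treated patients will no longer qualify; the documents do not allow that number to be estimated.

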8.8 Contraception

From the signing of informed consent on Visit 1 and throughout the duration of the study (until the last procedure at Visit 5) women of childbearing potential and men must use highly effective birth control methods.

A woman of childbearing potential is defined as a premenopausal female or a female who is less than 12 months post-menopausal and who has not undergone a

CONFIDENTIAL Page 42 of 88

hysterectomy or surgical sterilization, e.g. bilateral tubal ligation, bilateral ovariectomy (oophorectomy).

In this study the patients can use the following birth control methods:

- 1. Barrier methods:
 - Male condom + spermicide
 - Cervical cap + spermicide
 - Diaphragm + spermicide
- 2. Intrauterine device (IUD)
- 3. Intrauterine hormone-releasing system (IUS)
- 4. Hormonal contraceptives:
 - Hormonal implants
 - Hormonal injections
 - Combined Oral Contraceptive Pill
 - Mini pill
 - Birth Control Patch
- 5. Sexual abstinence.

Patients will be provided with information on acceptable methods of contraception as part of the informed consent process obtainment.

8.9 Treatment compliance

Intravenous treatment will be administered under the supervision of investigational site personnel and date, start and stop time, volume (mL) of each infusion will be documented in the eCRF. Oral dosing will be also performed under the supervision of investigational site personnel. The total amount of oral dosing completed (capsules count) as well as dose administered, date and time of dosing will be recorded in the eCRF.

Patients should be informed that compliance with taking all oral medication as instructed is imperative.

9 STUDY VISITS AND PROCEDURES

9.1 Schedule of study procedures

The time points at which each procedure and assessment will be performed are presented in study schedule of procedures/assessments (see Table 9-1).

CONFIDENTIAL Page 43 of 88

Table 9-1 Schedule of procedures/assessments

	Visit 1 ¹			Visit 2 ¹		Visit 3 ¹	Visit 4 ¹	Visit 5 ¹
Study procedures/assessments	Day 1 ²		Days 2-3(7)	Day 4(8)	Days 5(9)-7(14)	Within 1-2 days after the last dose ³	Within 7-9 days after the last dose ⁴	Within 21-23 days after the last dose
procedures, assessments	Screening procedures	Randomization and initiation of therapy	Continuation of intravenous therapy	Switch to oral therapy	Continuation of oral therapy	End of treatment visit	Test of cure visit	Long-term follow up visit
Initiation procedures								
Written informed consent (before all other procedures)	X							
Demographic data and other baseline characteristics	X							
Medical history	X							
Pregnancy test (for women of childbearing potential only)	X							
Check of inclusion/exclusion criteria	X							
Randomization (before starting of intravenous therapy)		X						
Safety assessments								
Physical examination	X		XXX ⁵	X ⁵	XXX ⁵	X	X	
Vital signs	X	X ⁶	XXX ⁶	X^6	XXX ⁶	X	X	
ECG (before or 30 minutes after blood samples collection)	X			X^5		X	X	
Haematology test	X ⁷			X^5		X	X	
Biochemical assay	X ⁷			X^5		X	X	

	Visit 1 ¹			Visit 2 ¹		Visit 3 ¹	Visit 4 ¹	Visit 5 ¹
Study procedures/assessments	Day 1 ²		Days 2-3(7)	Day 4(8)	Days 5(9)-7(14)	Within 1-2 days after the last dose ³	Within 7-9 days after the last dose ⁴	Within 21-23 days after the last dose
	Screening procedures	Randomization and initiation of therapy	Continuation of intravenous therapy	Switch to oral therapy	Continuation of oral therapy	End of treatment visit	Test of cure visit	Long-term follow up visit
Urinalysis	X ⁷		1.0	X^5		X	X	
Documentation of AEs/SAEs	X ⁸	X ⁸	XXX	X	XXX	X	X	X
Efficacy assessments								
Chest x-ray/ CT	X ⁹						X	
Pulse oximetry	X			X^5		X	X	
Sputum sample collection for culture (if the patient	X			X^5		X	X	
has sputum) Blood sample collection								
for culture	X			$X^{5, 10}$		X^{10}	X^{10}	
Clinical response assessment				X		X	X	
Infection relapse								X
assessment Pharmacokinetic paramete	wc.							
Blood sample collection for PK via venous catheter	15	X ¹¹						
IMP administration		1	1		•	1	1	
Start of intravenous therapy		X						
Daily intravenous therapy (at least 3 days and up to 7 days)			XXX					
Switch to oral therapy (first oral dose)				X ¹²				
Daily oral therapy (until					XXX			

	Visit 1 ¹			Visit 2 ¹		Visit 3 ¹	Visit 4 ¹	Visit 5 ¹
Study procedures/assessments	Day 1 ²		Days 2-3(7)	Day 4(8)	Days 5(9)-7(14)	Within 1-2 days after the last dose ³	Within 7-9 days after the last dose ⁴	Within 21-23 days after the last dose
	Screening procedures	Randomization and initiation of therapy	Continuation of intravenous therapy	Switch to oral therapy	Continuation of oral therapy	End of treatment visit	Test of cure visit	Long-term follow up visit
Day 7-14 of the study)								
Compliance check		X	XXX	X	XXX			
Other								
Prior/concomitant medication and therapies	X	X	XXX	X	XXX	X	X	X

X – All procedures should be performed during one day.

XXX – All procedures should be performed every day during mentioned period of time.

- 1 All procedures of Visit 1 and Visit 2 will be performed during patient's hospital stay. All procedures of Visit 3 and Visit 4 can be performed at outpatient department. Visit 5 will be conducted as a telephone contact.
- ² The maximum duration is 24 hours after the signing of informed consent.
- ³ The Visit should be conducted at least 24 hours after the last dose of the study drug.
- ⁴ All the efforts should be made to conduct this visit (Visit 4) 7 days after the end of treatment.
- ⁵ The procedure should be done before dosing.
- ⁶ On Day 1 of Visit 1 the procedure should be done 2 hours ±30 minutes after the infusion of second solution is finished. On Days 2-3(7) of Visit 1 the procedure should be done before dosing and 2 hours ±30 minutes after the infusion of second solution is finished. At Visit 2 the procedure should be done before dosing and 2 hours ±30 minutes after capsules intake.
- ⁷ At screening, during the study selection criteria assessment, the Investigator may use laboratory test results obtained at the laboratory of the investigational site within 24 hours of study enrollment (signing of the Informed Consent Form) if he / she considers that available data are sufficient to permit a decision on whether the subject meets the selection criteria. In this case, another blood sampling procedure has to be conducted in the period from the signing of the Informed Consent Form to the start of treatment in order to evaluate all other laboratory parameters that have to be determined on Day 1 in accordance with the study protocol.
- ⁸ The investigator will record in eCRF all AEs occurred after the first IMP administration and until the last procedure at Visit 5 and all SAEs occurred after the obtainment of the informed consent (after the signing of ICF) and until the last procedure at Visit 5.
- ⁹ Chest x-ray/ computed tomography (CT) may not to be done if the patient has the results of chest x-ray/ computed tomography that was performed within 72 hours before enrollment.
- ¹⁰ Blood sampling should not be conducted if no bacterial growth (negative culture) has been detected by blood cultures of samples withdrawn at Visit 1.
- Blood for drug concentration measurements will be withdrawn only in first 40 patients **in the investigational sites defined by the Sponsor**. The schedule for blood sample collection for the PK is as follows: pre-dose, 0 h, 0.5 h (±3min), 2.5h (±5min), 4h (±5min), 6h (±10min), 12h (±15min), 16h (±15min) and 22.5h (±15min) after the end of first infusion on Day 1. The last blood sampling for PK (22,5h after the end of the first infusion) should be conducted just prior to the IMP infusion on Day 2 of the study.

CONFIDENTIAL Page 46 of 88

¹² – The investigator will switch the patient to oral treatment if the patent meets criteria of clinical stability. If the treatment with intravenous IMP should be prolonged after the 7 days of treatment are completed (according to the investigator's opinion) the investigator should contact the study Medical Adviser for the approval of intravenous treatment prolongation. Please note that the first dose of oral drug will be administered on the day when the switch is performed (e.g. the patient will receive the first dose of oral drug on Day 4 if the switch is performed at Day 4, etc.).

CONFIDENTIAL Page 47 of 88

